### 1.3 Rationale for Study Design, Doses and Control Group

The purpose of this study is to assess subject treatment session perception and Investigator treatment experience when using Alluzience and powder BoNT-A. Both the investigational drug, Alluzience and the comparator, BOTOX®/Vistabel® (powder BoNT-A) are approved in the EU/EEA to treat glabellar lines. It is believed that a ready to use solution, such as Alluzience, might be advantageous compared to a vacuum dried powder, that needs to be reconstituted before use, when used in a clinical setting. This study and its assessments are therefore aimed at evaluating how the subjects and Investigator experiences the treatment session and the handling of the study product. **CCI**

The chosen dose of 20 U for powder BoNT-A was based on the dose recommended by the manufacturer. Note that the units for powder BoNT-A are specific to the preparation and are not interchangeable with other preparations of BoNT-A products.

The dose chosen for Alluzience is based on the evaluation of results for the different dose levels studied to date in the clinical program, where the Sponsor has concluded that a 50 s.U dose offers an appropriate balance between efficacy, duration of effect, and safety. 50 s.U is the approved dose for Alluzience for the treatment of GL as per the Summary of Products Characteristics.

### 1.4 Risk/Benefit Assessment

Both study products investigated in this trial are on the market in the participating countries and are considered safe for use in humans.

A majority of adverse reactions reported with Alluzience in clinical trials were of mild to moderate intensity and reversible. The most frequently reported adverse reactions were headache and injection site reactions. The incidence of adverse reactions tended to decrease with repeated treatments.

Adverse effects possibly related to the spread of toxin effect distant from the site of administration have been very rarely reported with botulinum toxin (excessive muscle weakness, dysphagia, aspiration pneumonia with fatal outcomes in some cases). Detailed adverse reaction information can be found in the Alluzience Summary of Products Characteristics.

Adverse reactions caused by BOTOX®/Vistabel® are similar to the expected adverse reactions listed above for Alluzience as both drugs are BoNT-A derivatives. Detailed adverse reaction information can be found in the BOTOX®/Vistabel® Summary of Products Characteristics.

The dose administered are according to the prescribing information for the study products in the EU/EEA. Therefore, the risks associated with participation in this study are considered acceptable compared to the anticipated high degree of subject satisfaction with treatment and the treatment regimen.

GALDERMA EST. 1981	Title 05PF2005 Clinical Study Protocol - STAR	Doc id MA-48441
-----------------------	---	---------------------------

## 2. CLINICAL STUDY OBJECTIVES, ENDPOINTS, AND CLINICAL HYPOTHESIS

### 2.1 Clinical Study Objectives

The objective of the study is to assess, subject treatment session perception and Investigator treatment experience when using Alluzience and powder BoNT-A. Additionally, efficacy and safety of a single dose of Alluzience, for the treatment of moderate to severe GL, will be evaluated during a 6-month follow-up period.

#### 2.1.1 Primary Objectives and Endpoints

The primary objective of this study is to evaluate the time needed to prepare Alluzience and powder BoNT-A according to protocol ([Appendix 1](#)).

#### 2.1.2 Secondary Efficacy Objective and Endpoints

1. **Objective:** To evaluate preparation/reconstitution experience of Alluzience and powder BoNT-A.

Endpoints:

- Proportion of study products prepared by the investigators in front of the patients.
- Proportion of answers within each answer option (strongly agree, agree, neither agree nor disagree, disagree and strongly disagree) to question comparing Alluzience preparation vs. powder BoNT-A reconstitution with regards to technical issues/problems.
- Proportion of treatment sessions where the Investigator answers that he/she have experienced issues with powder BoNT-A reconstitution.

See [Appendix 1](#) (Reconstitution/Preparation of Alluzience and powder BoNT-A) for details.

2. **Objective:** To describe Investigator treatment experience when using Alluzience for the treatment of GL.

Endpoints:

- Proportion of answers within each answer option (strongly agree, agree, neither agree nor disagree, disagree and strongly disagree) for each question specified in the Investigator Treatment Session Questionnaire ([Appendix 2](#))

CCI

GALDERMA EST. 1981	Title 05PF2005 Clinical Study Protocol - STAR	Doc id MA-48441
------------------------------	--	----------------------------------

Effective date: 2021-12-01 17:39

*Effective*

Version: 5.0

CCI

#### **2.1.4 Safety Objectives and Endpoints**

The safety objective is to evaluate the safety of a single dose of Alluzience for the treatment of moderate to severe GL.

**Endpoints:**

- Incidence, causality, severity, and duration of AEs collected during the study.

 GALDERMA EST. 1981	Title 05PF2005 Clinical Study Protocol - STAR	Doc id MA-48441
---	--	----------------------------------

### 3. OVERALL CLINICAL STUDY DESCRIPTION

This is an, open-label, randomized, interventional, two-armed, multi-centre study to investigate subject treatment perception and Investigator treatment experience when using Alluzience or vacuum-dried botulinum neurotoxin type A (powder BoNT-A) for treatment of GL.

Approximately 150 subjects will be randomized to either Alluzience or powder BoNT-A treatment in a **CCI** ratio. Randomization will be stratified by study site. It is estimated that around 170 subjects will be screened to obtain the number of randomized subjects needed for the study.

[figure not shown]
The study consists of six visits; screening, treatment and four follow-up visits 1, 3, 5 and 6 months after treatment, subjects randomized to be treated with powder BoNT-A will only be followed for 1-month (see [Table 1](#) and [Figure 1](#)). The screening visit and the treatment visit might be conducted at the same day. The Investigator and **CCI** will after the treatment answer questionnaires about how they perceived the treatment session and the Investigator will also answer questionnaires regarding treatment details, reconstitution and **CCI** of the used study product. **CCI**

Adverse events (AEs) will be collected from treatment until the follow-up visit. Any related, unresolved AE will be followed until resolution for up to 3 months after the study or until considered stable.

Efficacy assessments will include (Section [7.1](#)):

- Investigator Assessments:
  - Reconstitution/Preparation Questionnaire
  - Investigator Treatment Session Questionnaire

**CCI**

Safety assessments will include (Section [7.2](#)):

- AEs
- Pregnancy test

The selection criteria for the study population are described in Section [5](#). Detailed information about the study tasks for each study visit is outlined in Section [8](#) and in [Table 2](#). The treatment procedure is provided in Section [6.1.7.1](#).

### 4. CLINICAL STUDY DURATION AND TERMINATION

The planned duration of recruitment (from first subject first visit [FSFV] to last subject first visit [LSFV]) is approximately 3 months.

 EST. 1981	Title 05PF2005 Clinical Study Protocol - STAR	Doc id MA-48441
---	--	----------------------------------

The planned clinical study duration from FSFV to last subject last visit (LSLV) is approximately 9 months.

Clinical study participation is approximately 6.5 months for subjects in the Alluzience treatment group and 1.5 months for subjects in the powder BoNT-A treatment group, including the screening, treatment, and follow-up periods.

The Sponsor may decide to prematurely terminate or suspend the participation of a particular clinical study site (e.g., due to lack of subject enrollment or non-compliance with clinical study protocol (CSP), regulation, or GCP) or prematurely suspend the clinical study (e.g., for safety, study product quality, regulatory, efficacy, or logistical reasons) at any time with appropriate notification.

## 5. SELECTION AND DISPOSITION OF CLINICAL STUDY POPULATION

### 5.1 Number of Subjects

As a screen failure rate of approximately 10% is anticipated, approximately 170 subjects will be screened in order to enroll approximately 150 subjects in a **CC1** ratio to 50 s.U of Alluzience (N=100) or 20 U powder BoNT-A (N=50). It is expected that each site will recruit a similar number of subjects (approximately 10 to 20 subjects).

### 5.2 Clinical Study Population Characteristics

In order to be eligible for the clinical study, subjects must fulfill all of the following criteria. These criteria are applicable at both screening and baseline unless otherwise specified (note that 1 month = 4 weeks/28 days).

#### 5.2.1 Inclusion Criteria

Subjects must meet all the following criteria to be eligible for the study:

1. Female 18 to < 65 years of age.
2. Moderate to severe GL at maximum frown as assessed by the Investigator.
3. Female of non-childbearing potential (i.e., postmenopausal [absence of menstrual bleeding for 1 year prior to screening, without any other medical reason], or has undergone hysterectomy or bilateral oophorectomy).

OR

Female of childbearing potential with a negative urine pregnancy test at screening and baseline and agrees to use a highly effective and approved contraceptive method for the duration of the study. A highly effective method of contraception is defined as:

CONFIDENTIAL

Page 29 of 71

GALDERMA EST. 1981	Title 05PF2005 Clinical Study Protocol - STAR	Doc id MA-48441
-----------------------	---	---------------------------

Effective date: 2021-12-01 17:39

Effective

Version: 5.0

- Bilateral tubal ligation;
- Combined (estrogen and progesterone containing) oral, intravaginal or transdermal contraceptives that inhibit ovulation as the primary mode of action, on a stable dose for at least 28 days prior to screening visit;
- Hormonal or copper IUD inserted at least 28 days prior to Day 1;
- Partner vasectomized for at least three months prior to screening visit;
- Progestogen-only oral, injectable or implantable contraceptives that inhibit ovulation as the primary mode of action, on a stable dose for at least 28 days prior to screening visit; or
- Strict abstinence (i.e., refraining from heterosexual intercourse for the entire duration of the subject's participation in the study).

4. Time and ability to complete the study and comply with instructions.
5. Understands the study requirements and signed the informed consent form (ICF).
6. Subjects who have planned to undergo aesthetic facial treatment with powder toxin at the study site.
7. Previous use of any approved botulinum toxin in facial areas.

### 5.2.2 Exclusion Criteria

The presence of any of the following exclusion criteria excludes a subject from enrollment in the study:

1. Previous use of any botulinum toxin in facial area within 6 months prior to study treatment.
2. Female who is pregnant, breast feeding, or intends to conceive a child during the study.
3. Known allergy or hypersensitivity to any component of the investigational product or any botulinum toxin serotype.
4. Any known contraindication such as subject with bleeding disorder or subject currently using anticoagulants.
5. Previous use of any hyaluronic acid soft tissue augmentation therapy in the treated area within 3 months before baseline.
6. Previous soft tissue augmentation with any permanent (non-biodegradable such as silicone, polyacrylamide, etc) or semi-permanent (i.e., calcium hydroxylapatite, poly-L-Lactic acid or polymethyl-methacrylate) product; lifting threads, or autologous fat in the treatment area.
7. Subject has any prior or current psychiatric illness (e.g. Psychosis, depression, anxiety), alcohol or drug abuse, or is taking antidepressant, anxiolytic, or antipsychotic medication that, in the Investigator's opinion, could affect the subject's safety and/or participation in the study.

CONFIDENTIAL

Page 30 of 71

GALDERMA EST. 1981	Title 05PF2005 Clinical Study Protocol - STAR	Doc id MA-48441
-----------------------	---	---------------------------

Effective date: 2021-12-01 17:39

Effective

Version: 5.0

8. Other concurrent medical conditions, therapy, or other condition that, in the Investigator's opinion, would interfere with the evaluation of the study medication, safety or efficacy, and/or put the subject at risk if he/she participates in the study.
9. Participation in an investigational device or drug study within 30 days prior to study treatment or plans to enroll in any other investigational study during participation in this study.
10. Study site personnel, close relatives of the study site personnel (e.g. parents, children, siblings, or spouse), employees or close relatives of employees at the Sponsor company.

### **5.3 Medical History**

Relevant history of surgical events and medical conditions shall be documented in the subject's study file and electronic case report form (eCRF) using medical terminology.

### **5.4 Previous and Concomitant Therapies**

#### **5.4.1 Definition**

Previous therapies are defined as therapies that have been stopped within 4 weeks preceding the screening visit or within timeframes specified in the inclusion/exclusion criteria.

Concomitant therapies are defined as follows:

- any existing therapies ongoing at the time of the screening visit,
- any changes to existing therapies (such as changes in dose or formulation) during the course of the clinical study, or
- any new therapies received by the subject since the screening visit.

#### **5.4.2 Categories**

The following two categories are to be considered for previous and concomitant therapies:

- Drugs, including, but not limited to, prescription, over the counter, birth control pills/patches/hormonal devices, vitamins, herbal medicines/supplements, and homeopathic preparations.
- Medical and surgical procedures, including, but not limited to, laser/radiation procedures, dermal fillers (area of treatment should be indicated), X-rays, surgeries, other facial procedures, and tooth extractions.

 GALDERMA EST. 1981	Title 05PF2005 Clinical Study Protocol - STAR	Doc id MA-48441
---	--	----------------------------------

#### 5.4.3 Recording

Previous and concomitant therapies are to be recorded in the subject's source documents and eCRFs.

Concomitant therapies are to be reviewed at each visit and updated in the source documents and eCRFs as needed.

Any new concomitant therapy or modification of an existing therapy may be linked to an AE. A corresponding AE form should be completed to account for the change in therapy, except in some cases such as therapy used for prophylaxis, dose modification for a chronic condition, etc.

#### 5.4.4 Authorized Concomitant Therapies

Unless listed below under prohibited concomitant therapies (Section 5.4.5), all concomitant therapies are authorized.

#### 5.4.5 Prohibited Concomitant Therapies

The following therapies are prohibited since they may interfere with the efficacy and/or safety assessment of the study products:

- BoNT of any serotype.
- Any other investigational new drug or device.
- Any absorbable (temporary) or non-absorbable (permanent) material in the treatment area.
- Facial aesthetic procedures (e.g., ablative skin resurfacing, laser treatment, micro needling, photodynamic therapy, tattooing or chemical peel) or any other procedures in the treatment area.
- Facial surgery or eye surgery (including LASIK procedure).
- Medications that affect neuromuscular transmission such as curare-like depolarizing agents, lincosamides, polymyxins, anticholinesterases and aminoglycoside antibiotics.

If a prohibited therapy is necessary for the best clinical interest of the subject or due to safety reasons, the Medical Monitor should be notified, if time permits, to discuss possible alternatives prior to administration of a prohibited therapy (contact information for the Medical Monitor provided in the Investigator's site file).

If a subject receives a prohibited therapy during the clinical study, the Medical Monitor should be notified to discuss the subject's continuation in the clinical study (contact information for the Medical Monitor provided in the Investigator's site file). If possible, the subject should continue in the study for the scheduled follow-up visits.

GALDERMA EST. 1981	Title 05PF2005 Clinical Study Protocol - STAR	Doc id MA-48441
-----------------------	---	---------------------------

Effective date: 2021-12-01 17:39

Effective

Version: 5.0

## 5.5 Procedures/Reasons for Subject Discontinuation

An Investigator may decide to discontinue a subject from the clinical study for medical or safety reasons.

Although the importance of completing the entire clinical study should be explained to the subject by the clinical study personnel, any subject is free to discontinue participation in this clinical study at any time and for whatever reason, specified or unspecified, and without any prejudice. No constraints are to be imposed on the subject, and when appropriate, a subject may be treated with other conventional therapy when clinically indicated.

When a subject does not complete the clinical study, s/he will be fully assessed if such assessment is possible. The procedures designated for the Month 1 (powder BoNT-A treatment group) or the Month 6 (Alluzience treatment group)/Early Termination (ET) visit should be completed for all subjects discontinuing the clinical study and the appropriate eCRF should be completed.

All discontinuations and the reason for discontinuation are to be documented by the Investigator on the eCRF exit form. For discontinuation due to an AE, the AE form is to be completed. The Investigator should also ensure that the subject receives suitable therapy for the AE.

Potential reasons for discontinuation are listed below:

- Adverse Event: Complete an AE form.
- Withdrawal by Subject: Includes consent withdrawal, subject relocation, schedule conflicts, etc. Explain the reason for withdrawal in the comment section of the eCRF exit form.
- Lost to Follow-up: Confirmed by e.g., calling three times at different hours and leaving messages, if applicable, before declaring the subject lost to follow-up. Explain in the comment section of the eCRF exit form.
- Other: This category is to be used for a subject who discontinues due to a reason other than as specified in the predefined categories above. Explain the reason for discontinuation in the comment section of the eCRF exit form.

A subject who has been randomized and assigned a kit number/randomization number cannot be replaced by another subject if he/she discontinues the clinical study for any reason. Additional subjects may be enrolled (randomized/assigned to treatment) in order to attain the number of evaluable subjects. Under no circumstances shall subjects be enrolled more than once.

Pregnancies occurring during the screening period are considered screen failures; they should be recorded as such in the eCRF and no pregnancy form is to be completed.

For a pregnancy occurring after the screening period, follow the procedures described in Section 7.2.1.2.3. The subject may remain in the study, but no invasive procedure should be

	Title 05PF2005 Clinical Study Protocol - STAR	Doc id MA-48441
--	--	----------------------------------

conducted. The Sponsor may also decide to prematurely terminate or suspend a subject's participation in the clinical study.

## 6. CLINICAL SUPPLIES

### 6.1 Clinical Supply Identification and Use

At the baseline visit, each subject will receive a single treatment divided equally among 5 injection points (0.1 mL per injection point) in the glabellar region with either Alluzience or powder BoNT-A according to his or her randomization assignment. For details regarding the treatment procedure, refer to Section [6.1.7.1](#).

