Strength/Concentration:	10 U/0.05 mL per injection point. In total 50 s.U in 0.25 mL for 5 injection points.	
BOTOX®/Vistabel®:	BOTOX®/Vistabel® is a botulinum toxin type A, supplied in a sterile, vacuum-dried form. The vial, containing 50 U, is reconstituted with 1.25 mL of sterile, 0.9% sodium chloride before study treatment.	

GALDERMA EST. 1981	Title 05PF2005 Clinical Study Protocol - STAR	Doc id MA-48441
-----------------------	---	---------------------------

Strength/Concentration:	4 U/0.1 mL per injection point. In total 20 U in 0.5 mL for 5 injection points.
Treatment area/Indication:	Glabellar lines
Treatment regimen and injection procedure:	Single treatment at the baseline visit, with either Alluzience or powder BoNT-A administered according to each products SmPC.
Statistical Method:	CCI
Sample Size:	The sample size of approximately 150 subjects, 100 subjects in the Alluzience treatment group and 50 in the powder BoNT-A treatment group, is not based on a statistical calculation. The selected number of subjects is regarded as sufficient for an evaluation of the studied endpoints by using descriptive statistics.
Interim Analysis:	No interim analysis will be performed.

GALDERMA <small>EST. 1981</small>	Title 05PF2005 Clinical Study Protocol - STAR	Doc id MA-48441
--------------------------------------	---	---------------------------

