#### 6.1.1 Alluzience

The investigational product Alluzience will be supplied as a liquid in a vial containing 125 s.U of Alluzience at a concentration of 200 U/mL. The drug product should be stored at the recommended temperature (between +2°C and +8°C) should not be frozen. Keep vials in the outer carton in order to protect from light. Each vial contains 0.625 mL of deliverable volume of solution. A volume of 0.25 mL, containing 50 s.U of Alluzience, will be withdrawn from the vial into a syringe for subject administration.

Details of the drug composition and excipients are provided in the current SmPC for Alluzience[16,59](#).

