### 6.1.3 Study Products Description

**Table 5 Description and Usage of the Study Products**

	Investigational product	Reference product
Name of drug substance	AbobotulinumtoxinA	OnabotulinumtoxinA
Name of investigational product/ reference product	Alluzience	BOTOX®/Vistabel®
Pharmaceutical form	Solution for injection	Vacuum-dried powder
Concentration	200 s.U/mL, each vial contains 125 s.U in 0.625 mL of solution ready for use, 10U/0.05 mL per injection point	50 U/vial Diluted in 0.9% sodium chloride before use to 4 U/0.1 mL per injection point
Buffer composition	CCl	N/A
Packaging	Glass vial	Glass vial
Reconstitution	N/A	1.25 mL (0.9% NaCl solution)
Storage conditions	2-8°C	2-8°C
Dosage	50 s.U 0.25 mL total 0.05 mL per injection point	20 U 0.5 mL total 0.1 mL per injection point
Route	Intramuscular injection	Intramuscular injection
Dose regimen	Single treatment at baseline visit	Single treatment at baseline visit
Location of treated area	Glabellar region	Glabellar region

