#### 6.1.7.1 Treatment Procedure

Prior to injection, the treatment area should be cleaned with a suitable antiseptic solution. An appropriately sized syringe and needle should be used to administer the treatment. The needle size (gauge) used by the Investigator in the study should be collected.

[figure not shown]
Treatment of the glabellar region with Alluzience or powder BoNT-A is administered as an intramuscular injection, given as 0.05 mL per injection point for Alluzience (0.25 mL in total), and

	Title 05PF2005 Clinical Study Protocol - STAR	Doc id MA-48441
--	--	----------------------------------

given as 0.1 mL per injection point for powder BoNT-A (0.5 mL in total), using an appropriately sized syringe and needle.

The 5 injection sites include 2 injections into each corrugator supercilii muscle, and 1 injection into the procerus muscle. Before injection, place the thumb or index finger firmly below the orbital rim in order to prevent extravasation below the orbital rim. The needle bevel should be pointed upward and medially during the injection. In order to reduce the risk of ptosis, avoid injections near the levator palpebrae superioris muscle, particularly in patients with larger brow-depressor complexes (depressor supercilii). Injections should be made into the central part of the corrugator muscle, at least 1 cm above the orbital rim. The recommended injection points for GLs are shown below in Figure 2.

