**Figure 2 Injection Sites for Treating Glabellar Lines**

#### **6.1.7.2 Treatment Regimen**

Each subject will receive a single treatment with 50 s.U Alluzience, 20 U of powder BoNT-A at the baseline visit. The total injection volume for Alluzience is 0.25 mL in 5 injection points, i.e. 0.05 mL (10 s.U) per injection point. The total injection volume for powder BoNT-A is 0.5 mL in 5 injection points, i.e. 0.1 mL (4 U) per injection point.

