### 8.1.2 Baseline/Treatment, Visit 2 (Day 0)

If the screening and baseline visits are performed on the same day, the study assessments that are common to both study visits will only be performed once (i.e., AE, concomitant therapies/procedures, UPT, inclusion/exclusion review). A maximum of 21 days is allowed between the screening and baseline visits.

At the baseline visit, the Investigator or designee (*Note: the treating investigator must perform both the reconstitution/preparation and the treatment*) will:

1. Ask the subject about any changes in his/her concomitant therapies/procedures (added, removed or changed) since the previous visit. Record changes in concomitant therapies/procedures as appropriate (Section 5.4).
2. If the subject is a female of childbearing potential, collect urine for pregnancy test and document the test result (see Section 7.3.2). A negative result is required for study inclusion.
3. Investigator reviews the inclusion/exclusion criteria (Section 5.2.1 and 5.2.2), and confirm whether or not the subject meets study eligibility requirements.
  - If yes, enroll/randomize the subject in the clinical study. Proceed to the next steps.

GALDERMA EST. 1981	Title 05PF2005 Clinical Study Protocol - STAR	Doc id MA-48441
-----------------------	---	---------------------------

Effective date: 2021-12-01 17:39

Effective

Version: 5.0

- If no, document the subject as a screen failure.

4. For subjects who meet all eligibility requirements, the Investigator will receive notification of the subject's randomization assignment.
5. Take subject photographs (see Section 7.3.1) for future GAIS assessments according to separate photography manual. If the subject is wearing make-up, instruct the subject to remove it prior to taking the photographs.
6. Make sure to equilibrate Alluzience, or the saline used for reconstitution of powder BoNT-A, for 30 min to room temperature before injection.
7. Ask the subject to complete the Subject Satisfaction Questionnaire (Appendix 6). **Note:** must be performed before treatment.
8. The Investigator should prepare Study Product according to the assigned treatment in the same room and in front of the subject (Section 6.1.7).
9. Prior to injection, clean the subject's treatment area with a suitable antiseptic solution.
10. The Investigator will administer treatment. See Section 6.1.7.1 for injection technique and treatment procedure requirements.

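### Protocol 6.1 gives 0.1 mL per injection point for both products; for Alluzience this implies 0.5 mL and 100 s.U, twice the intended 0.25 mL and 50 s.U

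*Protocol*

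**What the plan says.** The opening paragraph of Protocol section 6.1 sets one per-point volume and names both products: "divided equally among 5 injection points (0.1 mL per injection point) in the glabellar region with either Alluzience or powder BoNT-A". Its next sentence refers to 6.1.7.1 for the details of the procedure.

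Every other place that states the Alluzience volume gives half of that per point, or a total that matches half:

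- Synopsis, strength/concentration of Alluzience: "10 U/0.05 mL per injection point. In total 50 s.U in 0.25 mL for 5 injection points".
- Section 6.1.1: "A volume of 0.25 mL, containing 50 s.U of Alluzience, will be withdrawn from the vial into a syringe for subject administration".
- Table 5 (section 6.1.3), dosage row: "50 s.U 0.25 mL total 0.05 mL per injection point".
- Section 6.1.7.1: 0.05 mL per point and 0.25 mL in total for Alluzience, set beside 0.1 mL and 0.5 mL for powder BoNT-A.
- Section 6.1.7.2: "The total injection volume for Alluzience is 0.25 mL in 5 injection points, i.e. 0.05 mL (10 s.U) per injection point".

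Section 1.3 identifies 50 s.U as the approved dose for glabellar lines, and section 6.3.5 rules out dose modification.

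**The concern.** The parenthesis in 6.1 cannot be true of both products, because they are injected at different volumes. Taken literally for Alluzience, it doubles the volume at each point and so doubles the dose relative to the approved 50 s.U. The risk/benefit statement in section 1.4 rests on dosing within the prescribing information, so the literal reading would also fall outside that argument.

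Two features of the protocol do nothing to stop the misreading. The Alluzience vial holds 0.625 mL, so 0.5 mL can physically be withdrawn. Section 6.1.7 also describes the injection procedure as the same in both groups, which sits badly next to a shared 0.1 mL figure.

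There is a smaller consequence for reporting. SAP 12.1 lists whether each injection followed the protocol, and SAP 7.5 has study product use as a deviation type. With two per-point volumes in the protocol, that judgement has no single standard.

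What is at stake is patient safety and clear dosing text. The primary endpoint, preparation time, is not defined by the volume injected at each point.

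**Working it through.** **Inputs**

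| Quantity | Value | Source |
|---|---|---|
| Alluzience vial | 125 s.U in 0.625 mL | Synopsis; 6.1.1; Table 5 |
| Alluzience drawn up | 0.25 mL = 50 s.U | 6.1.1 |
| Alluzience per point | 0.05 mL | Synopsis; Table 5; 6.1.7.1; 6.1.7.2 |
| Per point, either product | 0.1 mL | 6.1 |
| Powder BoNT-A reconstitution | 50 U in 1.25 mL | Synopsis; Table 5; Appendix 1 |
| Number of points | 5 | All of the dosing sections except 6.1.1, which gives only the draw-up |

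Section 6.1.1 writes the concentration in U ("supplied as a liquid in a vial containing 125 s.U of Alluzience at a concentration of 200 U/mL"), while the synopsis and Table 5 write s.U. I take both to mean Speywood units.

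**Formula.** Dose = number of points x mL per point x concentration.

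**1. Reproduce the plan's own Alluzience dose.**
- Concentration: 125 s.U / 0.625 mL = 200 s.U/mL.
- Per point: 0.05 mL x 200 s.U/mL = 10 s.U.
- Total: 5 x 0.05 mL = 0.25 mL, and 0.25 mL x 200 s.U/mL = 50 s.U. This matches the stated figures exactly.

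**2. Reproduce the plan's own powder dose.**
- Concentration: 50 U / 1.25 mL = 40 U/mL.
- Per point: 0.1 mL x 40 U/mL = 4 U.
- Total: 5 x 0.1 mL = 0.5 mL, and 0.5 mL x 40 U/mL = 20 U. This also matches. The 0.1 mL in 6.1 is therefore the powder volume.

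**3. Apply 6.1 as written to Alluzience.**
- Per point: 0.1 mL x 200 s.U/mL = 20 s.U.
- Total: 5 x 0.1 mL = 0.5 mL, and 0.5 mL x 200 s.U/mL = 100 s.U.
- Ratio to the stated dose: 100 / 50 = 2.0.

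**4. Can 6.1 and 6.1.1 both be followed?**
- The 0.25 mL draw-up at 0.1 mL per point serves 0.25 / 0.1 = 2.5 points, but 6.1 requires equal division among 5. The shortfall is 0.5 - 0.25 = 0.25 mL.
- At 0.05 mL per point it serves 0.25 / 0.05 = 5 points exactly.
- So the two sections cannot be carried out together, and all the other dosing text shows that 6.1 is the one in error.

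**5. Does the vial prevent the error?** No: 0.5 mL is less than the 0.625 mL in the vial.

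**The case against.** The best case for leaving this alone is that 6.1 states no dose at all. It gives no units, no total volume and no concentration. The 100 s.U appears nowhere in the protocol and arises only when the per-point volume in 6.1 is multiplied by the concentration given elsewhere. Wherever the Alluzience dose is stated, it is 50 s.U.

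The surrounding text also steers sites to the right volume. Section 6.1 itself points to 6.1.7.1, which sets out the two volumes side by side. Step 10 of Visit 2 does the same: "The Investigator will administer treatment. See Section 6.1.7.1 for injection technique and treatment procedure requirements". The syringe is meant to hold 0.25 mL. Section 6.1.7 requires administration according to each product's SmPC, by investigators who are trained in the technique and experienced in this indication. To overdose a subject, a site would have to draw up twice the volume in 6.1.1 and disregard 6.1.7.1, 6.1.7.2 and Table 5.

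Most of this stands. The doubled dose is implied rather than stated, and the chance of harm is low. It is also fair to call this an inconsistency of text, since none of the protocol's stated totals is miscalculated. None of it makes the sentence in 6.1 correct: that sentence names Alluzience explicitly and assigns it the wrong volume, in the section that governs clinical supplies and their use.

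**Conclusion.** The concern holds. As written, section 6.1 implies 0.5 mL and 100 s.U of Alluzience, exactly twice the 0.25 mL and 50 s.U given or implied by every other dosing statement, and it cannot be reconciled with the 0.25 mL draw-up in 6.1.1. The most likely explanation is that the powder volume was written once for both arms.

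The factor of 2 rests only on the 200 s.U/mL concentration, which the protocol states and which the vial contents confirm. That 6.1 is the faulty passage is an inference from the agreement of all the other sections and from the approved dose in 1.3.

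This should be fixed because it concerns dose. The practical risk is limited, and nothing in the sample size, the endpoint definitions or the analysis depends on it.

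**What to change.** Replace the parenthesis in Protocol 6.1 with volumes by product: 0.05 mL at each point for Alluzience and 0.1 mL at each point for powder BoNT-A. The totals then become 5 x 0.05 mL = 0.25 mL (50 s.U) and 5 x 0.1 mL = 0.5 mL (20 U), in line with the rest of the protocol. Send sites a short note confirming the Alluzience volume.

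The cost is one line of protocol text, handled under the amendment process in section 10.5.2, and a brief site communication. No change to the SAP is required. If the eCRF records injected volume or units, naming those fields in SAP 12.1 would be a useful addition. The eCRF is not among the documents reviewed, so this is optional and the main correction does not depend on it.
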